In 1999, the Anderson Orthopaedic Research Institute (AORI) initiated a prospective, Institutional Review Board-approved study to compare the clinical outcome of total hip arthroplasty (THA) patients who were randomized to either crosslinked Marathon or non-crosslinked Enduron polyethylene liners. During an 18-month enrollment period, 226 patients who received 236 THAs consented to participate in the study. Six patients (6 THAs) were excluded intra-operatively, leaving 230 THAs implanted with a Duraloc acetabular shell (DePuy) coupled with a 28-mm cobalt-chrome femoral head (DePuy). At 5-year outcome, we found that crosslinked Marathon polyethylene liners were wearing 95% less than the non-crosslinked Enduron liners [1]. In fact, the Marathon wear rates were so low at 5-year follow-up that the mean was not statistically different than zero. Several other institutions have also reported very low wear rates with highly crosslinked polyethylene based on early clinical outcome data [2-8]. However, since osteolysis typically appears after 5-year follow-up, the reduction in the incidence and extent of periprosthetic bone loss among THA patients with Marathon liners, compared to those with Enduron liners, was not as dramatic as the wear reduction [9]. Despite the substantial reduction in wear that we observed at 5-year follow-up, the patients' perceptions of their outcomes remained similar among the Marathon and Enduron groups [1]. At an average follow-up interval of at least 10-years (using outcome data for individual study participants obtained at a minimum of 9-year follow-up), we anticipated that the reduction in wear associated with Marathon polyethylene would be associated with significant reductions in periprosthetic osteolysis. Our findings [10] confirmed this hypothesis and indicated that the wear rate of Marathon polyethylene remained substantially lower than conventional Enduron polyethylene through 10-year follow-up.

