Because crosslinking is accompanied by a reduction in the ultimate tensile strength, fatigue strength, and elongation to failure of ultra high molecular weight polyethylene [11-13], characterizing the long-term clinical performance of Marathon polyethylene is also important. Concerns have been expressed about the potential for the liner fracture, *in vivo* polyethylene oxidation or accelerated wear at long-term follow-up, the effects of femoral head roughening over time and the bioreactivity of crosslinked polyethylene debris particles [14-23]. Ultimately, the best way to address these concerns is in the context of well-controlled, long-term clinical outcome studies. As part of our efforts to follow patients throughout their lives to obtain long-term outcome data, we will continue to obtain routine follow-up at 5-year intervals from the date of surgery for each patient. Because we anticipate that the reduced incidence of wear and osteolysis will result in a lower incidence of revision surgery among the patients randomized to Marathon liners, implant revision for reasons related to wear will be our primary outcome measure at long-term follow-up.

Primary Hypothesis:

- Primary THAs prospectively randomized to Marathon liners will demonstrate a lower rate of revision for wear-related complications and higher survivorship compared to primary THAs randomized to Enduron liners.

Additional Hypotheses:

- Primary THAs prospectively randomized to Marathon liners will demonstrate substantially reduced polyethylene wear compared to primary THAs randomized to Enduron liners.
- THAs prospectively randomized to Marathon liners will demonstrate a reduced incidence of clinically important osteolysis with an area of at least 1.5 square centimeters compared to primary THAs prospectively randomized to Enduron liners.
- THAs prospectively randomized to Marathon liners will demonstrate higher rates of patient satisfaction and better Harris Hip Scores compared to primary THAs randomized to Enduron liners.
- All the THAs prospectively randomized to Marathon and Enduron liners will demonstrate constant wear rates over time.

Study Population

Inclusion criteria

- Patient consented to participate in this study
- Implanted on the acetabular side with a Duraloc 100 cup incorporating a 4-mm lateralized polyethylene liner that was randomized to either Marathon or Enduron

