- Implanted on the femoral side with an extensively porous-coated (AML/Solution or Prodigy) stem with a 28-mm cobalt-chrome femoral head

Exclusion criteria

- Intra-operative considerations related to implant stability, leg length correction or bone quality led to the implantation of THA components other than a Duraloc 100 cup, 4-mm lateralized liner, extensively porous-coated stem and 28-mm cobalt-chrome femoral head
- Patient refused reconsent for continued follow-up

Anticipated Study Population Size

The 230 THAs randomized to a Marathon or Enduron polyethylene liner will comprise the study population for our survivorship analyses. Based on our previously published data, we found 9 THAs among deceased patients at a mean follow-up of 5.7 years [1] and 32 THAs among deceased patients at a mean follow-up of 10 years [10]. Based on this data, we anticipate that approximately 12% of the patients enrolled in the study will pass away every five years.

Material and Methods:

- Patients due for routine 15-year follow-up will be contacted by Anderson Orthopaedic Institute personnel who will schedule follow-up appointments. Attempts will be made to obtain follow-up for all enrolled patients who have not had a follow-up evaluation at the Anderson Clinic within one year before the 15-year anniversary of their original surgery date. This procedure will be repeated at five-year intervals (20 years, 25 years, etc.).

Study interval	Minimum follow-up date for study interval	End date
15-year	DOS + 14 years	DOS + 19 years -1 day
20-year	DOS + 19 years	DOS + 24 years -1 day
25-year	DOS + 24 years, etc.	DOS + 29 years -1 day, etc.
Continue every 5 years		

- At the initial follow-up visit associated with this long-term study, the subjects will be informed of changes to the protocol and asked to sign a reconsent.
- At the time of each follow-up visit, patients will complete the clinic patient questionnaire per current protocols and the physician will complete a standardized evaluation.
- Standardized x-rays will be obtained during follow-up visits per current standard of care.

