- Serial x-rays for each THA will be analyzed to identify regions of femoral and acetabular osteolysis. The area of each osteolytic region will be measured on the AP pelvic x-ray with Martell's Hip Analysis Suite software. The incidence of osteolysis will be compared using a chi-square or Fisher's Exact test, depending on the cell counts. The size of osteolytic lesions will be compared using an Independent samples t-test or Mann-Whitney U, depending on the normality of the data. X-rays will also be used to evaluate radiographic complications such as periprosthetic fracture and implant loosening. The incidence of radiographic complications among the Marathon and Enduron groups will be compared using a chi-square or Fisher's Exact test, depending on the cell counts.
- Kaplan-Meier survivorship analysis will be used to compare the outcome of the Marathon and Enduron groups using revision for any reason as an endpoint. Survivorship analyses using revision for specific diagnoses, such as wear and osteolysis or implant loosening, will also be performed.
- Clinical outcome data among the Marathon and Enduron groups will be queried from AORI's institutional database and compared based on the nature and distribution of the data. Specifically, we anticipate that patient satisfaction will be compared with a Fisher's Exact test and Harris Hip scores will be compared with the use of a Mann-Whitney U.
- A manuscript summarizing the results of this study will be submitted for publication in a peer-reviewed orthopaedic journal. The results of this study will also be presented at orthopaedic meetings and conferences.
- Subjects will continue to be followed for life.

Source of Funding

Partial funding for this study will be provided by DePuy Orthopaedics. Study costs in excess of the funding provided by DePuy will be supported internally by the Anderson Orthopaedic Research Institute.

References

1. Engh CA Jr, Stepniewski AS, Ginn SD, Beykirch SE, Sychterz-Terefenko CJ, Hopper RH Jr, Engh CA. A randomized prospective evaluation of outcomes after total hip arthroplasty using cross-linked marathon and non-cross-linked Enduron polyethylene liners. *J Arthroplasty*. 2006 Sep;21(6 Suppl 2):17-25.

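### Does the plan leave open whether wear-related or any-reason revision decides the primary hypothesis?

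*Combined protocol and SAP*

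**What the plan says.** Three places in the combined protocol and SAP bear on this.

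- The untitled background section, just before the hypotheses, declares the outcome: "implant revision for reasons related to wear will be our primary outcome measure at long-term follow-up".
- The Primary Hypothesis says that hips given Marathon liners "will demonstrate a lower rate of revision for wear-related complications and higher survivorship compared to primary THAs randomized to Enduron liners". It does not say which event survivorship is measured to.
- The survivorship bullet in Material and Methods says "Kaplan-Meier survivorship analysis will be used to compare the outcome of the Marathon and Enduron groups using revision for any reason as an endpoint", and continues: "Survivorship analyses using revision for specific diagnoses, such as wear and osteolysis or implant loosening, will also be performed".

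The documents give no list of the diagnoses that count as wear-related. They also give no significance level, power, expected number of revisions or multiplicity rule for any revision endpoint. The 230 hips named under Anticipated Study Population Size are the hips enrolled less the intra-operative exclusions (236 - 6 = 230), not the result of a sample-size calculation.

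**The concern.** A reader who goes straight to the survivorship bullet finds any-reason revision first and wear and osteolysis only as an example among further analyses. With a hypothesis in two parts, that reader could take the decisive result to be wear-related revision alone, both endpoints together, or whichever succeeds.

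The readings have different consequences. Revisions unrelated to the liner dilute a wear effect, so requiring both endpoints would lower power. Accepting either would raise the false-positive rate. If wear-related revision alone decides, the answer could depend on whether loosening or liner fracture is counted. Fracture is raised in the background as a worry about crosslinked liners ("Concerns have been expressed about the potential for the liner fracture"), so its coding could fall mainly on one arm. Wear and osteolysis results to 10 years were also already known when this text was written ("Our findings [10] confirmed this hypothesis and indicated that the wear rate of Marathon polyethylene remained substantially lower than conventional Enduron polyethylene").

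**Working it through.** **Step 1: do the passages conflict?**

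| Question | Background | Primary Hypothesis | Survivorship bullet |
|---|---|---|---|
| Which outcome is primary? | Wear-related revision | Wear-related revision comes first | Ranks nothing |
| Is wear-related revision analysed? | – | – | Yes, under specific diagnoses |
| Is any-reason revision analysed? | – | – | Yes |
| Survivorship to which event? | – | Not stated | Both kinds are run |

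No cell contradicts another. The bullet is silent on rank and the background supplies it. Survivorship in the hypothesis follows directly on a sentence that makes wear-related revision primary. It can be read as survival free of that event, in which case the two parts nearly coincide. The any-reason reading is an inference from the bullet.

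**Step 2: what could the choice of endpoint cost?** There is no stated figure to reproduce. The inputs from the documents are 230 hips and mortality ("we anticipate that approximately 12% of the patients enrolled in the study will pass away every five years"). Assumed: 115 hips per arm, 15 years, two-sided 5%, exponential event times and all revision rates. Log-rank simulation, with non-wear revisions at 2-8% in both arms:

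| Wear revision, Enduron vs Marathon | Power, wear-related | Both significant |
|---|---|---|
| 6% vs 1% | 47-48% | 13-27% |
| 10% vs 3% | 50-51% | 21-36% |
| 10% vs 1% | 83-85% | 38-65% |
| 15% vs 1% | 98% | 71-92% |

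A repeat of this simulation agreed to within about two percentage points.

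A closed-form check shows the dilution. Let Enduron have w wear revisions, each arm o other revisions, and the wear hazard ratio be h. Then the any-reason hazard ratio is (w·h + o)/(w + o), and power is Φ(|ln HR|·√(d/4) − 1.96), where d is the number of events.

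- Wear-related, w = 8, h = 0.2: d = 8 × 1.2 = 9.6, and power = Φ(1.609 × 1.549 − 1.96) = Φ(0.53) = 0.70.
- Any reason, o = 4: HR = (1.6 + 4)/12 = 0.47, d = 9.6 + 8 = 17.6, power 0.36.
- Any reason, o = 16: HR = (1.6 + 16)/24 = 0.73, d = 9.6 + 32 = 41.6, power 0.17.

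The direction is certain, but the size is set by the assumed rates.

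**Step 3: false positives.** If either endpoint could be claimed, the error is 1 − P(|Z₁| < 1.96, |Z₂| < 1.96), with correlation equal to the square root of the wear share of all revisions:

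- wear share 25%, correlation 0.50: 9.1%
- wear share 50%, correlation 0.71: 8.3%
- wear share 75%, correlation 0.87: 7.3%

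The bound under independence is 1 − 0.95² = 9.75%. With one decisive endpoint, or with both required, the error is at most 5%. The hypothesis joins its parts with 'and', so the 7-9% belongs to a rule the plan does not state.

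**Step 4: the boundary of wear-related.** The bullet names wear and osteolysis, and implant loosening, as examples of specific diagnoses; it does not pool them. The background links the concerns about crosslinked polyethylene to reduced strength and lists fracture, oxidation and accelerated wear as separate items, which points away from coding fracture as wear. The documents give no fracture rate, so a calculation of its effect on power would rest on an invented figure. The earlier results that the background reports by arm are wear and osteolysis, not revisions by cause.

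**The case for a change.** The strongest case for a change is that the only survival-analysis text leads with an endpoint that is not the declared primary and relegates the primary to an example in an open list. No list says which diagnoses qualify, and some wear and osteolysis results by arm are already known. Under the assumed rates the two analyses would differ in significance in roughly 7-47% of trials, so a reader of the eventual paper might want to know in advance which one governs. The remedy would be a few words and would need no new data.

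Part of this stands. The bullet does not repeat the priority, the event behind survivorship is unstated, and wear-related has no diagnosis list. It does not follow that the primary result is undetermined. Different results on a cause-specific and an all-cause endpoint are to be expected when one is a subset of the other, and the declared primary says which to read first. Requiring both to succeed would in effect make any-reason revision co-primary, against the declared outcome. Reporting any-reason revision alongside, which guards against disputes over coding, is already planned.

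**Conclusion.** The concern does not call for a change. The background identifies wear-related revision as the primary outcome, the methods provide a survivorship analysis for it, and any-reason revision is also analysed. Followed as written, the plan reports both results and the primary one can be identified. The gaps in labelling and definition are details that analysts would fill sensibly: treat wear-related revision as decisive, state the qualifying diagnoses, and show any-reason revision beside it as the result that does not depend on coding.

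No figure in the documents is contradicted. The illustrative sizes (power of about 47-98% for wear-related revision, about 13-92% if both endpoints had to succeed, and 7-9% false positives if either sufficed) rest on assumed revision rates, equal allocation and a 5% level. The last two also need decision rules that the plan does not adopt. The conclusion would be different if the methods named any-reason revision as primary, or if the hypothesis allowed success on either endpoint. They do neither.

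### Revision is analysed by Kaplan-Meier only; within each arm 1−KM overstates the share of hips actually revised, so cumulative incidence should be reported beside it

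*Combined protocol and SAP*

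**What the plan says.** The survivorship bullet in Material and Methods states: "Kaplan-Meier survivorship analysis will be used to compare the outcome of the Marathon and Enduron groups using revision for any reason as an endpoint". It adds: "Survivorship analyses using revision for specific diagnoses, such as wear and osteolysis or implant loosening, will also be performed". Cumulative incidence, competing risks and the handling of deaths are not mentioned anywhere.

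The background, just before the hypotheses, says that "implant revision for reasons related to wear will be our primary outcome measure at long-term follow-up", and expects less wear and osteolysis to "result in a lower incidence of revision surgery among the patients randomized to Marathon liners". The Primary Hypothesis joins two quantities: Marathon hips "will demonstrate a lower rate of revision for wear-related complications and higher survivorship".

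On mortality, Anticipated Study Population Size reports 9 hips in deceased patients at a mean of 5.7 years and "32 THAs among deceased patients at a mean follow-up of 10 years". It concludes: "we anticipate that approximately 12% of the patients enrolled in the study will pass away every five years". The survivorship population is 230 hips. Material and Methods ends by committing to lifelong follow-up.

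**The concern.** Survivorship and incidence of revision are different quantities once many patients die with the implant in place. Kaplan-Meier with deaths censored estimates implant survival as if nobody died. Its complement, 1−KM, is therefore a net risk. The share of hips in this cohort that come to revision is the cumulative incidence, which is lower because a hip whose patient has died can no longer be revised. The plan names an estimator for the first quantity and none for the second.

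At stake is the absolute reporting: the revision percentage in each arm and, under conditions given below, the difference between arms that tells a reader how many revisions the liner avoids. The primary outcome is exposed more than any-reason revision, for two reasons. The background notes that "since osteolysis typically appears after 5-year follow-up", so wear-related revisions would tend to fall in the years when mortality is higher. In a diagnosis-specific curve, revision for another reason would also be censored.

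**Working it through.** **1. The plan's 12%.** Between the two looks there are 32 − 9 = 23 more hips in deceased patients over 10 − 5.7 = 4.3 years.
- Linear, over 230 hips: (23/230) × 5/4.3 = 11.6% per five years.
- Linear, over the 221 hips remaining: (23/221) × 5/4.3 = 12.1%.
- Constant hazard: 1 − (198/221)^(5/4.3) = 12.0%.

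The figure reproduces. It describes the later period: averaged from surgery, 32/230 over ten years is 7.0% per five years. So the observed counts are used to year 10 and 12% only after that.

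**2. Mortality curve, S(t) = fraction alive.** The death hazard is −ln(221/230)/5.7 = 0.00700 per year to 5.7 years, then −ln(198/221)/4.3 = 0.02556 per year to 10 years. The mean follow-up times are used as interval ends, which is an approximation. After year 10 there are two readings of the 12%:
- *Higher:* 12% of those enrolled, S(t) = 198/230 − 0.024(t − 10). Dead at 15, 20 and 25 years: 26%, 38%, 50%.
- *Lower:* 12% of survivors, the hazard staying at 0.02556. Dead: 24%, 33%, 41%.

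**3. Formulas.** With revision hazard h(u) and cumulative hazard H(u):
- 1−KM(t) = 1 − exp(−H(t))
- Cumulative incidence(t) = ∫₀ᵗ h(u) · exp(−H(u)) · S(u) du

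**4. Revision patterns (all assumed).** The 20-year 1−KM is set at 5% and at 20%. Any-reason revision has a constant hazard from year 0, or 40% or 60% of the 20-year cumulative hazard in the first two years. Wear-related revision has a constant hazard from year 5.

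Example, 1−KM of 20% at 20 years, higher mortality:
- Any reason: h = −ln(0.80)/20 = 0.01116 per year; cumulative incidence 17.1%; ratio 1.17; gap 2.9 points.
- Wear: h = −ln(0.80)/15 = 0.01488 per year from year 5; cumulative incidence 16.1%; ratio 1.24; gap 3.9 points.

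At a 1−KM of 5% the cumulative incidences are 4.2% and 4.0%, with gaps of 0.8 and 1.0 points.

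**5. Ratio of 1−KM to cumulative incidence, death as the only competing event.**

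| Assumed pattern | Mortality | 15 y | 20 y | 25 y |
|---|---|---|---|---|
| Any reason, constant | higher | 1.11 | 1.17–1.18 | 1.25–1.26 |
| Any reason, 40% early | higher | 1.06–1.07 | 1.11–1.12 | 1.17–1.18 |
| Any reason, 60% early | higher | 1.04 | 1.07–1.08 | 1.11–1.12 |
| Wear, from year 5 | higher | 1.16 | 1.24–1.25 | 1.33–1.35 |
| Any reason, constant | lower | – | 1.16–1.17 | 1.22–1.23 |
| Wear, from year 5 | lower | – | 1.22–1.23 | 1.29–1.30 |

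If the wear hazard rises linearly after year 5 instead of staying level, the 20-year ratio is about 1.31 even at the lower mortality.

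**6. Other-cause revision also censored.** Multiplying the integrand by exp(−r·u), with r assumed at 0.25%, 0.5% or 1% per year, raises the 20-year wear ratio (higher mortality) to about 1.28, 1.32 or 1.40.

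**7. Difference between arms at 20 years (higher mortality, all rates assumed).**
- Same timing and mortality in both arms, 1−KM of 20% against 5%: 15.0 points by 1−KM; by cumulative incidence 12.8 (any reason) or 12.1 (wear).
- Different timing, 20% with 40% early against 15% starting at year 5: 5.0 points by 1−KM, 18.03 − 12.07 = 5.96, about 6.0, by cumulative incidence.
- Different mortality, both wear-shaped, 20% against 15%, death hazards multiplied by 0.8 and 1.2 (32% and 44% dead): 5.0 points by 1−KM, 16.8 − 11.6 = 5.2 by cumulative incidence.

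The first case narrows the difference. The other two widen it.

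**8. Sampling error.** In simulation with an assumed 230/2 = 115 hips per arm and a true 20-year 1−KM of 20%, the standard deviation of 1−KM was 4.0 to 4.3 points, so a 95% interval is about ±8 points.

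**The case against.** The best reply is that nothing in the plan is wrong. The stated purpose is to characterise the long-term performance of the polyethylene, and net survivorship is the right quantity for that. The hypothesis does include higher survivorship. No sentence says that 1−KM will be presented as the share of hips revised, and the references to a lower rate and a lower incidence are directional. The size depends on revision rates, timing and other-cause rates that the documents do not give. The year-5 start for wear revision borrows from a remark about osteolysis. The gap is smaller than sampling error.

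Most of this stands, and it rules out three stronger readings that a reader might infer:
- *That Kaplan-Meier is the wrong method or biases the comparison of arms.* It is valid for net survivorship, and censoring deaths leaves a cause-specific comparison unaffected.
- *That 1−KM always exaggerates the difference between arms.* Step 7 shows two cases in which it does not. They are illustrations, not predictions, and the documents give neither mortality nor revision timing by arm.
- *That the plan commits to misreporting incidence.* It is silent on how absolute rates will be presented and on how deaths are handled.

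What remains is that the hypothesis speaks of a rate of revision as well as of survivorship, and only survivorship has an estimator. Within an arm the direction of the gap does not depend on the assumed rates. It is systematic, so a larger sample would not remove it.

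**Conclusion.** The point holds as a cheap improvement to reporting, not as an error in the plan. If deaths are censored, 1−KM overstates the share of hips revised within each arm, and increasingly so with follow-up. At 20 years, for an assumed 1−KM of 5% to 20% and 33% to 38% dead, the ratio is about 1.07 to 1.18 for any-reason revision, at the low end if revisions cluster early. It is about 1.22 to 1.25 for wear-related revision starting at year 5 with a level hazard, and higher if other-cause revision is censored too. The absolute difference between arms is overstated in the same way if mortality and revision timing are similar in both arms, but not necessarily otherwise.

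**What to change.** In the survivorship bullet of Material and Methods:
- Keep Kaplan-Meier, label it net implant survivorship, and state that deaths are censored.
- Beside it, report the Aalen-Johansen cumulative incidence of revision by arm and the between-arm difference, with 95% confidence intervals at 15, 20 and 25 years.
- Treat death as a competing event for every revision endpoint. For diagnosis-specific endpoints, including the wear-related primary outcome, treat revision for other reasons as a further competing event.

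The cost is a few sentences and one more analysis in standard software. It needs dates of death, where the plan shows only counts. Material and Methods foresees subjects who cannot be contacted; deaths among them may be missed, which would leave some overstatement. The absolute rates reported will be slightly smaller.

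### Fisher's exact test is anticipated for patient satisfaction whatever the counts; if dissatisfaction is rare, Boschloo's exact test gains power at the same 5% ceiling

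*Combined protocol and SAP*

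**What the plan says.** The clinical-outcome bullet of Material and Methods says that outcomes will be "compared based on the nature and distribution of the data", and then that "we anticipate that patient satisfaction will be compared with a Fisher's Exact test". No cell-count condition is attached, but the wording is an expectation and not a fixed rule. The coding of satisfaction is not given.

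The two radiographic comparisons are planned differently. "The incidence of osteolysis will be compared using a chi-square or Fisher's Exact test, depending on the cell counts", and radiographic complications follow the same rule. The cell-count threshold is not stated.

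Higher satisfaction with Marathon is listed under Additional Hypotheses. The document gives no significance level, sidedness, expected rate, effect size or power for any of these comparisons. It does not mention an interval for a difference in proportions.

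On numbers, the Anticipated Study Population Size section says "The 230 THAs randomized to a Marathon or Enduron polyethylene liner will comprise the study population for our survivorship analyses". It reports "32 THAs among deceased patients at a mean follow-up of 10 years" and adds that "we anticipate that approximately 12% of the patients enrolled in the study will pass away every five years".

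**The concern.** Fisher's test conditions on the total number of events. With few events only a few tables are possible, so the attainable p-values are coarse and the real false-positive rate can fall far below the nominal level. The trial fixed the arm sizes, not the total number of dissatisfied patients, so an unconditional exact test suits the sampling.

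The loss matters because the cohort is closed. Enrolment ended long ago and deaths reduce the numbers at every follow-up interval, so power cannot be bought with more patients. If most patients in both arms are satisfied, an over-conservative test makes a real difference more likely to be reported as none.

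**Working it through.** The plan has no figure of its own to reproduce, so the check enumerates every possible 2x2 table.

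**Arm size at 15 years.** The split by arm is not given; equal arms are assumed.
- From 230 hips with 12% deaths per five years: 230 × (1 − 0.36) = 147.2, or 74 per arm. Compounded, 230 × 0.88³ = 156.7, or 78 per arm.
- From the reported 32 deaths at 10 years: 230 − 32 = 198. Then 198 − 0.12 × 230 = 170.4, or 85 per arm; or 198 × 0.88 = 174.2, or 87 per arm.
- These are upper limits before other losses. The calculations use 60, 80 and 100 per arm, with 85 as an extra case.

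**Other assumptions.** Two-sided 5% level, independent hips, satisfaction coded yes/no.

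**Method.** Let x₁ and x₂ be the numbers dissatisfied among n per arm. Fisher's p sums the hypergeometric probabilities no larger than that of the observed table, given x₁ + x₂. For a rejection region R,

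P(reject) = Σ over R of Bin(x₁; n, π₁) × Bin(x₂; n, π₂).

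This is the real size when π₁ = π₂ and the power otherwise. Fisher's region is p ≤ 0.05. Boschloo's region is p ≤ c, where c is the largest cutoff whose size stays at or below 0.05 for every common π. Fisher's own size never exceeds 0.05, so c is at least 0.05 (at 60 per arm it is 0.0665). Boschloo's region therefore contains Fisher's, and its power cannot be lower.

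**Satisfaction, dissatisfaction rare**

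| Hips per arm | Size at 5% v 5%: Fisher | Boschloo | Power, 98% v 90% satisfied: Fisher | Boschloo |
|---|---|---|---|---|
| 60 | 1.1% | 2.7% | 28% | 40% |
| 80 | 1.6% | 3.3% | 44% | 55% |
| 100 | 2.1% | 2.9% | 59% | 63% |

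At 85 per arm, power for the same contrast rises from 48% to 58%. Boschloo's maximum size over all common rates is 4.9% to 5.0%.

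**Dependence on the event rate, 80 per arm**

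| Common event rate | Expected events in total | Fisher size | Boschloo size |
|---|---|---|---|
| 2% | 3 | 0.2% | 1.0% |
| 5% | 8 | 1.6% | 3.3% |
| 10% | 16 | 2.8% | 3.9% |
| 20% | 32 | 3.2% | 4.6% |
| 50% | 80 | 3.3% | 4.8% |

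With 115 per arm and a 50% rate, Fisher reaches 4.1%. The gain in power at 80 per arm also narrows: 5% v 15% goes from 48.1% to 53.3%, and 10% v 25% from 64.8% to 70.7%.

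**Worked example.** With 1 v 7 dissatisfied of 80 each, Fisher gives p = 0.064 and Boschloo p = 0.048. (In software that takes columns as the groups, a transposed table gives 0.032, which is not the p-value for this comparison.)

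**Radiographic outcomes under the planned rule.** Assume Fisher is used when any expected count is below 5, and chi-square otherwise. For an event in 2% v 12%:

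| Hips per arm | Chi-square selected | Fisher alone | Planned rule | Boschloo |
|---|---|---|---|---|
| 60 | 33% | 43% | 49% | 55% |
| 80 | 69% | 62% | 68% | 70% |
| 100 | 90% | 76% | 82% | 79% |

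The rule is about 6 points behind Boschloo at 60, 2 behind at 80, and ahead at 100. Its maximum size at these arm sizes is 5.2% to 5.6%, slightly above nominal.

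**The case against.** Fisher's test is valid, familiar and errs on the safe side. The choice between conditional and unconditional testing is an old dispute: under randomisation inference with a sharp null the event total is fixed, which favours Fisher. If satisfaction has more than two levels, Fisher's test extends to it and Boschloo's 2x2 test does not. All of this stands. It makes the point an improvement and not the correction of an error, and it limits the fix to a two-level outcome.

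A reader might infer more than the documents support:
- *That Fisher will always be used.* The bullet says the authors anticipate it and leaves the choice to the data.
- *That the real error rate is 1–2% in general.* That holds for roughly 6 to 12 events in total. The document gives no rates, and over plausible inputs the range is about 0% to 4%.
- *That Boschloo restores a full 5%.* It guarantees at most 5% and is also conservative when events are few: 1.0% at a 2% rate with 80 per arm.
- *That the radiographic comparisons lose as much.* Setting Fisher alone against Boschloo for 2% v 12% suggests losses of 12, 8 and 3 points, but the plan does not use Fisher alone there.
- *That the background shows a null being misread.* The statement that "the patients' perceptions of their outcomes remained similar among the Marathon and Enduron groups" is a one-line summary of a cited 5-year report. The document does not say which test or interval lay behind it.

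**Conclusion.** The point holds for patient satisfaction, as a modest and nearly free gain. If about 2% to 10% are dissatisfied, with 60 to 100 hips per arm, Boschloo's test adds about 4 to 12 points of power for 98% v 90% satisfied, and about 10 at the 80 to 85 per arm that deaths alone might leave at 15 years. If dissatisfaction is common, the gain is around 5 points. For osteolysis and radiographic complications the planned rule already recovers most of the power, so the case for change is weak.

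The result rests on an assumed two-sided 5% level, equal arms, a two-level outcome and assumed rates. It also assumes independent hips. The background reports 226 consenting patients with 236 hips (236 − 226 = 10 more hips than patients), and neither test allows for pairing. The hypothesis concerned is an additional one, and the primary revision endpoint is untouched.

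**What to change.** In the clinical-outcome bullet of Material and Methods:
- State how satisfaction is coded, the significance level and the sidedness.
- If it has two levels, name Boschloo's unconditional exact test in advance. If it has more, keep Fisher's test in its extended form.
- Report the difference in proportions with a 95% score interval (Miettinen–Nurminen or Newcombe).

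For osteolysis and radiographic complications, using Boschloo in place of Fisher when cells are small is optional. If the present rule stays, state its cell-count threshold.

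The cost is a change of wording. No new data are needed and the test is in standard software. The one downside is that orthopaedic readers know it less well than Fisher's test.
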